4 INVESTIGATIONAL PLAN

4.1 Overall Study Design

This is an open-label, multi-center Phase Ib/II, study of BBI608 administered in combination with TMZ to patients with recurrent or progressive GBM who have not received prior bevacizumab therapy. The study is designed to explore the safety, tolerability and pharmacokinetics of BBI608, and the preliminary anti-cancer activity of BBI608 in combination with TMZ, in adults with recurrent or progressive GBM who have not received prior treatment with bevacizumab and who may or may not be eligible for further surgical resection. The primary efficacy endpoint will be PFS-6. Secondary efficacy endpoints will include median PFS, OS, DCR and ORR.

Arm A will include patients who are candidates for repeat surgical resection. These patients will receive 7 (\pm 2) days of BBI608 monotherapy at a dose level of 480 mg twice daily (960 mg total daily dose – Initial Dose) prior to resection. Following surgical clinical recovery, and on a date between 15-28 days following the date of surgery, BBI608 (480 mg twice daily) will be restarted in combination with TMZ (150 mg/m² on days 1 through 5 of each 28-day cycle). If a patient does not recover from surgical resection sufficiently within 28 days to resume oral therapy with BBI608 plus TMZ, the patient should be withdrawn from study. Combination therapy will continue until disease progression or another discontinuation criterion is met. The dose of TMZ can be increased to 200 mg/m² for those patients who complete at least one cycle at 150 mg/m² in combination with BBI608.

Arm B will include patients who are either not candidates for repeat surgical resection or have undergone repeat surgical resection prior to enter the study. These patients will receive BBI608 (480 mg twice daily) in combination with TMZ (150 mg/m² administered for days 1 through 5 of each 28 day cycle) and continue treatment until disease progression or another discontinuation criterion is met. The dose of TMZ can be increased to 200 mg/m² for those patients who complete at least one cycle at 150 mg/m² in combination with BBI608.

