5.4.2 Surgical Resection of Recurrent GBM

ONLY patients enrolled into Arm A will undergo surgical resection of GBM.

BBI608 will be administered for 7 (\pm 2) days prior to a planned surgical resection of recurrent GBM. BBI608 will be administered on the morning of the surgical procedure (Run-in Week 2 Day 8) and BBI608 will remain held pending clinical post-operative recovery of the patient as determined by the investigator, for up to 28 days after surgery. Tumor sample will be obtained at time of surgical resection from T1/gadolinium enhanced lesion(s) as well as T2/FLAIR infiltrating tumor lesions and will be used to investigate BBI608 presence in the resected tumor tissue and will be used for pharmacodynamics analysis (please see the Laboratory Manual for additional information). Additionally, blood sample will be obtained at time of surgery to evaluate BBI608 pharmacokinetic (PK) exposure in the plasma (please see the Laboratory Manual for additional information). The time of BBI608 administration on the day of surgery and the collection times of blood sample will be recorded.

Tumor samples that are obtained at the time of surgical resection and are labeled with study protocol identification number and patient identification number will be sent to a regulatory authority-approved tumor bank affiliated with the study site, or to the study site pathology department if the site does not have a regulatory authority-approved tumor bank. In the event

that there is difficulty with establishment of histological diagnosis, tumor tissue will be made available to the pathology department at all study sites. Processing of all tumor tissue will include creation of both fresh frozen samples for PK analysis as well as blocks of formalin fixed paraffin-embedded (FFPE) samples for PD analysis.

An MRI will be performed 48-72 hours following surgery and will be used as the baseline scan for the purposes of tumor response evaluation in the patients who undergo surgical resection.

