For patients in Arm A during the run-in period with BBI608 monotherapy, the same DLT rules as for the combination therapy will apply. Enrollment will be held if ≥ 2 of 6 patients are unable to undergo resection due to DLTs. Enrollment will also be held if ≥ 2 of 6 patients have an unexpected surgical complication.

Initial enrollment will be to a 6-patient safety cohort in each arm. These patients will be evaluated for the occurrence of DLT during the first 28 days of combination treatment with BBI608 and TMZ. If DLT is observed in ≥ 2 of 6 patients evaluable for DLT, the initial dose of BBI608 for all patients in that arm will be reduced to the next lower dose level of 240mg twice daily, and an additional 6-patient safety cohort will be enrolled at that dose-level and evaluated for DLT as above. Enrollment will continue at a dose-level at which ≤ 1 of 6 patients experiences DLT. Dose modification is allowed according to the standard schedule for BBI608.

Cycles of therapy will consist of the patient taking BBI608 daily in combination therapy for 28 days. Tumor assessments will be performed every two cycles (eight weeks), or as otherwise clinically indicated.

The RP2D is defined as the dose level at which no more than one patient with DLT is observed among six patients. Once the RP2D has been reached for a given arm based on

DLT assessment rules outlined above, up to 24 additional evaluable patients may be enrolled at RP2D.

It is expected that up to 30 patients (including those enrolled to the DLT evaluation cohorts) will be enrolled in each arm.

Phase II

In both Phase Ib and Phase II, a study cycle will consist of 28 days of daily administration of BBI608 and TMZ administration on days 1-5 of each cycle. Pharmacokinetic (PK) and pharmacodynamic assessments will be performed in the first cycle only. Safety and tolerability of BBI608 in combination with TMZ will be assessed for the duration of the study treatment and for 30 days after the last dose of BBI608. Evaluation of anti-tumor activity of BBI608 in combination with TMZ will be performed at 8-week intervals while patients remain on study according to RANO.

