The duration of follow-up is defined as time from the date of first dose of study treatment to the death or last known visit. If a subject dies, the duration is equal to date of death minus study start + 1 with censor variable =1 (censored for follow up). If a subject is alive, the duration is equal to the date subject last known to be alive minus study start + 1 with censor variable=0 (event for follow up).

Extent of Exposure

Exposure may be summarized (overall and by period for Arm A subjects) as dose received (cumulative dose or actual dose intensity) or as dose received relative to intended dose (relative dose [RD], or relative dose intensity [RDI]), or both.

The information that will be summarized depends on how the study drug is dosed (e.g., infusion cyclical, oral daily, oral cyclical).

In what follows “time unit” can be e.g., weeks or days.

Drug accountability will be summarized in a listing.

Intended treatment duration = intended end of treatment date – date of first dose of study drug +1, where the intended end of treatment date is (start date of last cycle + intended cycle duration – 1 day) for each treatment arm

- For BBI608, intended cycle duration= $\max\{28, \text{date of last dose of the cycle} - \text{date of first dose of the cycle} + 1\}$
- For BBI608 in pre-surgical period for Arm A patients, intended cycle duration= surgical procedure date – first dose date + 0.5. Subjects in Arm A took BBI608 in the morning of the surgical procedure and thus took a half day’s dose of BBI608.
- For cyclic combination drug TMZ, intended cycle duration=5 days

Actual treatment duration = actual end of treatment date – date of first dose of study drug +1,

- For BBI608 and TMZ, actual end of treatment date is last dosing date

Cumulative dose in a period (for Arm A subjects), cycle, or overall for BBI608 is the sum of the actual doses received in a period or cycle or overall, respectively. Cumulative dose overall for TMZ is the sum of the actual doses received overall.

Actual Dose Intensity [DI]

- For Arm A subjects: By period actual DI (*dose unit/week*) = [cumulative dose in the period]/[intended period duration in weeks]
- By cycle actual DI (*dose unit/week*) = [cumulative dose in cycle] / [intended cycle duration in *weeks*].
- Overall actual DI (*dose unit/week*) = [overall cumulative dose] / [intended treatment duration in *weeks*].

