4. Daily treatment compliance will be reported for each patient for the following dose-levels and intervals
 - The % of days the patient received a total dose of at least 960 mg BBI608 out of intended treatment duration in days.
 - The % of days the patient received a total dose of at least 480 mg BBI608 out of intended treatment duration in days.
 - The % of days the patient received a non-zero dose of BBI608 out of intended treatment duration in days.

Daily treatment compliance will be grouped according to the following categories: < 60%, ≥ 60% - < 80%, ≥ 80% - < 90%, ≥ 90%, and will be summarized for the treatment group of BBI608 Plus TMZ and BBI608 (for pre-surgery period for Arm A).

Combination drug compliance overall

5. Overall: For TMZ, compliance will be calculated using the following equation: (Number of treatments administered /number of treatments that should have been administered) x 100= % compliance

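### Daily compliance in the Arm A run-in divides whole dosing days by a duration that counts surgery day as half a day, so full adherence does not score 100% and some patients with missed days fall in the wrong category

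*SAP*

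**What the plan says.** Four statements combine.

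- **Dosing.** Protocol 4.1 gives the run-in dose as "480 mg twice daily (960 mg total daily dose – Initial Dose) prior to resection". Protocol 5.4.2 sets the run-in at 7 days, plus or minus 2, and places a final morning dose on the day of surgery (Day 8 of the nominal schedule).
- **Run-in duration.** SAP 8.2.1, Extent of Exposure, defines "intended cycle duration= surgical procedure date – first dose date + 0.5" and gives the reason: "Subjects in Arm A took BBI608 in the morning of the surgical procedure and thus took a half day’s dose of BBI608".
- **Intended treatment duration.** The same section builds this from the cycle duration, "where the intended end of treatment date is (start date of last cycle + intended cycle duration – 1 day) for each treatment arm".
- **Daily compliance.** SAP 8.2.1, Treatment compliance item 4, reports three day counts over that duration: days at 960 mg or more, days at 480 mg or more, and days with any dose. The last reads "The % of days the patient received a non-zero dose of BBI608 out of intended treatment duration in days". Results are grouped as below 60%, 60 to below 80%, 80 to below 90%, and 90% or above. They are summarised for the combination and, separately, for the Arm A pre-surgery period.

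Item 4 gives no denominator of its own for the pre-surgery period and no cap at 100%.

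**The concern.** A count of days cannot contain half a day. On surgery day the numerator gains either a whole day (any dose, or at least 480 mg) or nothing (at least 960 mg), while the denominator gains half a day. Two measures are therefore pushed up and the third is pushed down, within one table. Programmed literally, the table can show compliance above 100%, and patients near a cut-point can change category. SAP 2.1 expects up to 30 patients per arm, so each moved patient shifts a cell by at least 1/30, or 3.3 percentage points.

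There is a second, smaller gap. The run-in formula needs a surgical procedure date, and the plan expects some Arm A patients to have none. SAP 2.1 states "Enrollment will be held if ≥ 2 of 6 patients are unable to undergo resection due to DLTs", and the Protocol synopsis says how Arm A patients who are not resected are to be assessed for response. For them the run-in duration, and every ratio built on it, is undefined.

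**Working it through.** The documents state no compliance percentage to reproduce, so the SAP formula is first checked on its own ground, the dose-based ratio.

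**Inputs.** n full dosing days before surgery, with n = 5 to 9 (Protocol 5.4.2); 960 mg per full day (Protocol 4.1); 480 mg on surgery morning (half the daily dose, SAP 8.2.1); duration n + 0.5 (SAP 8.2.1); category limits from item 4. Both doses are assumed taken on Day 1.

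**Step 1: dose-based compliance, n = 7.** (7 × 960 + 480) / (7.5 × 960) = 7200/7200 = 100%. The half day is right for this use.

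**Step 2: carry-through to item 4.** With the run-in as the only cycle, intended treatment duration = (start + 7.5 − 1) − start + 1 = 7.5 days.

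**Step 3: full adherence.** Days at 960 mg or more = n. Days at 480 mg or more = days with any dose = n + 1.

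| n | Denominator | At least 960 mg: n/(n + 0.5) | At least 480 mg, and non-zero: (n + 1)/(n + 0.5) |
|---|---|---|---|
| 5 | 5.5 | 90.9% | 109.1% |
| 6 | 6.5 | 92.3% | 107.7% |
| 7 | 7.5 | 93.3% | 106.7% |
| 8 | 8.5 | 94.1% | 105.9% |
| 9 | 9.5 | 94.7% | 105.3% |

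Every entry is in the 90% or above category.

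**Step 4: whole days missed, non-zero and at-least-480 mg measures.** SAP result (n + 1 − m)/(n + 0.5) against whole-day result (n + 1 − m)/(n + 1), with m days missed.

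- n = 7, m = 1: 7/7.5 = 93.3% against 7/8 = 87.5%; one category too high.
- n = 7, m = 2: 6/7.5 = 80.0% against 6/8 = 75.0%; one category too high.
- m = 1 for n = 5, 6 and 8: 90.9%, 92.3% and 94.1% against 83.3%, 85.7% and 88.9%; each one category too high.
- n = 9, m = 0 to 4: no change of category.

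**Step 5: days below 960 mg, at-least-960 mg measure.** SAP result (n − m)/(n + 0.5) against (n − m)/n, with surgery day left out because it cannot reach 960 mg and m full days below 960 mg.

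- n = 5, m = 1: 4/5.5 = 72.7% against 4/5 = 80.0%; one category too low.
- n = 6, m = 1: 5/6.5 = 76.9% against 5/6 = 83.3%; one category too low.
- n = 7 and n = 9, m = 0 to 4: no change of category.

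**Step 6: run-in at 240 mg twice daily, n = 7.** SAP 2.1 provides for a reduced starting dose of 240 mg twice daily. If the run-in followed it, full adherence would give 8/7.5 = 106.7% on non-zero, 7/7.5 = 93.3% on at least 480 mg, and 0% on at least 960 mg.

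**The case against.** The strongest reply is that little follows from this, and much of that reply stands.

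- **Adherent patients are not misclassified.** A reader might infer from scores of 107% and 93% that fully adherent patients land in the wrong category. They do not: the lowest full-adherence value is 90.9%. A shift needs whole missed days or, for the 960 mg measure, days below that dose. On the non-zero and at-least-480 mg measures, skipping single evening doses changes nothing.
- **The comparator is partly a choice.** The 80.0% in the 5-day example leaves surgery day out. If it is counted, 4/6 = 66.7% falls in the same category as the SAP's 72.7%. Item 4 also uses fixed dose levels and is not built to read 100% for every adherent patient. This limits the 960 mg examples. It does not rescue scores above 100% on the other two measures.
- **The denominator is inferred.** The SAP does not say in words that the pre-surgery table uses the run-in's own duration. It is nevertheless the natural reading, since the only duration given for that period is the one with the half day.
- **Patients without surgery.** A reader might infer that those who could not tolerate the run-in drop out of the exposure summary, so that tolerability is overstated. The SAP states no such exclusion. The full analysis set takes everyone with one dose (SAP 6.1). Cumulative dose and actual treatment duration need no surgery date. Discontinuation reasons, DLT listings and adverse events leading to held, reduced or stopped drug are all reported. What remains is an undefined denominator.

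**Conclusion.** The point holds as a mismatch of units in one descriptive table. Under 480 mg twice daily, both doses on Day 1 and the run-in's own duration as denominator, full adherence over 5 to 9 days scores 105.3% to 109.1% on two measures and 90.9% to 94.7% on the third. Some patients with missed or reduced days move by one category, upward on the first two measures and downward on the 960 mg measure; the downward shift also depends on leaving surgery day out.

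The documents do not support going further. No efficacy or DLT result depends on this table, SAP 4.1 plans no hypothesis tests, and the dose-based compliance in item 1 is correct. For patients without surgery, the finding is only that the formula has no value for them. This is a minor correction, worth making before the table is programmed.

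**What to change.** **Item 4, pre-surgery period.** Use whole-day denominators. Count surgery day as one full day for the non-zero measure and for any threshold that the patient's assigned morning dose can meet; otherwise exclude it. At 480 mg twice daily with n = 7, full adherence becomes 8/8, 8/8 and 7/7. Tying the rule to the assigned dose matters: a fixed denominator of 8 for the 480 mg threshold would score an adherent patient on 240 mg twice daily at 7/8 = 87.5%, whereas the rule gives 7/7.

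**Dose-based measures.** Keep the half-day duration for dose intensity, relative dose, relative dose intensity and compliance items 1 to 3. State explicitly which duration each pre-surgery measure uses.

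**Arm A patients without surgery.** Name a fallback end date that the trial records. A planned surgery date would serve only if it is collected, which neither document shows. The last dosing date is a poor substitute, because the denominator would end when dosing ended and early stopping would be hidden.

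**Cost.** A few sentences in SAP 8.2.1 and a small programming change. The item 4 change uses only the first dose date, surgery date and assigned dose. No visit or treatment changes.

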Relative dose [RD]: The basic intent is to evaluate dose per *week* factoring in dose reductions or interruptions.

- Relative dose by period (Arm A subjects), by cycle and overall
 - By period RD (%) = $100 \times [\text{cumulative dose in the period}] / [\text{intended cumulative dose per period}]$
 - By cycle RD (%) = $100 \times [\text{cumulative dose in the cycle}] / [\text{intended cumulative dose per cycle}]$
 - Overall RD (%) = $100 \times [\text{overall cumulative dose}] / [\text{total planned or intended dose}]$
- For a combination regimen
 - if a study drug is discontinued prematurely while other study drug(s) are continued, then the RD is 0 for the discontinued study drug until all other study drug(s) of the regimen are discontinued

Relative Dose Intensity (RDI): The basic intent is to evaluate dose per *week* factoring in dose reductions, interruptions, or delays.

- Relative dose intensity (RDI) by period (Arm A subjects), by cycle and overall
 - Intended DI (*dose unit/week*) = [intended cumulative dose per period/cycle] / [intended number of *weeks* in a period/cycle]
 - By period RDI (%) = $100 \times [\text{by period actual DI}] / [\text{intended DI}]$
 - By cycle RDI (%) = $100 \times [\text{by cycle actual DI}] / [\text{intended DI}]$
 - Overall RDI (%) = $100 \times [\text{overall actual DI}] / [\text{intended DI}]$

Note:

- The intended dose level is fixed at the start of treatment rather than the start of a cycle.

- The intended cumulative dose of BBI608 per period (for Arm A subjects) is calculated by (intended dose level per day) x (intended period duration in days).
- The intended cumulative dose of BBI608 per cycle is calculated by (intended dose level per day) x (intended cycle duration in days).
- Dose unit of BBI608 is mg; dose unit of TMZ is mg/m².

Treatment compliance

BBI-608 compliance will be summarized by period (for Arm A), for cycle 1 (Arm A post-operative and Arm B patients) and overall

1. By Period (Arm A): Treatment compliance for BBI-608 is defined as below, (Cumulative actual total dose per period/ total planned or intended dose per period) x 100=% compliance
2. By Cycle (Arm A post-operative and Arm B): Treatment compliance for BBI608 is defined as below, (Cumulative actual total dose per cycle /total planned or intended dose per cycle) x 100= % compliance
3. Overall: Treatment compliance for BBI-608 is defined as below, (Cumulative actual total dose /total planned or intended dose) x 100= % compliance

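### SAP 8.2.1: overall relative dose intensity, if reported, falls below 100% for fully dosed, undelayed patients, both for TMZ and for BBI608 in Arm A

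*SAP*

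**What the plan says.** All references are to SAP 8.2.1 unless noted.

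- **Duration.** Intended treatment duration runs from the first dose of study drug to an intended end date, "where the intended end of treatment date is (start date of last cycle + intended cycle duration", less one day). The cycle length in that formula is at least 28 days for BBI608. For TMZ the text is "For cyclic combination drug TMZ, intended cycle duration=5 days".
- **Arm A run-in.** A separate length applies: "For BBI608 in pre-surgical period for Arm A patients, intended cycle duration= surgical procedure date" less the first dose date, plus 0.5, because the last run-in dose is the morning dose on the day of surgery.
- **Dose intensity (DI).** Overall actual DI is the ratio "overall cumulative dose] / [intended treatment duration in *weeks". Overall RDI divides that by an intended DI, which is defined per period or per cycle only.
- **Doses.** "Cumulative dose overall for TMZ is the sum of the actual doses received overall". A formula for the intended cumulative dose is given for BBI608 only: "The intended cumulative dose of BBI608 per cycle is calculated by (intended dose level per day) x (intended cycle duration in days". Also, "The intended dose level is fixed at the start of treatment rather than the start of a cycle".
- **Daily compliance (item 4).** Three percentages use the intended treatment duration as denominator, for example "The % of days the patient received a non-zero dose of BBI608 out of intended treatment duration in days". They are summarized for a BBI608-plus-TMZ group and, in Arm A, for the pre-surgery period.
- **Schedule (SAP 2.1, Protocol 4.1).** TMZ is given on five days of each 28-day cycle. The Arm A run-in is 7 ± 2 days, and BBI608 restarts 15 to 28 days after surgery.

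**The concern.** RDI is meant to show dose lost through reductions, interruptions or delays. A patient with none of these should score 100%. The overall formula counts planned drug-free days in the denominator of actual DI but not in intended DI. For TMZ these are the 23 off-days of every cycle except the last. For Arm A BBI608 they are the days between surgery and restart.

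A table built this way would show TMZ delivery of 20 to 30% in patients who took every dose from two to six cycles. It would also show lower BBI608 delivery in Arm A than in Arm B only because Arm A has planned surgery.

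**Working it through.** The SAP states no exposure figure to reproduce, so the check puts a fully dosed, undelayed patient through its formulas.

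**TMZ**

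Inputs: 150 mg/m² on 5 days per cycle, cycles starting every 28 days, k cycles. The SAP gives no intended cumulative dose for TMZ. The schedule gives 150 × 5 = 750 mg/m² per cycle. The span is taken to start at the first TMZ dose.

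- Span = 28(k−1) + 5 days.
- Actual DI = 750k / (span/7) mg/m² per week.
- Intended DI on the SAP's 5-day cycle = 750 / (5/7) = 1,050 mg/m² per week.
- Overall RDI = 5k / (28(k−1) + 5).

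| Cycles | Span (days) | Overall RDI |
|---|---|---|
| 1 | 5 | 5/5 = 100% |
| 2 | 33 | 10/33 = 30.3% |
| 3 | 61 | 15/61 = 24.6% |
| 6 | 145 | 30/145 = 20.7% |

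If the first dose of study drug instead means run-in day 1 in Arm A, the one-cycle span with a 7-day run-in is 7 + 15 + 5 = 27 to 7 + 28 + 5 = 40 days. RDI is then 5/27 = 18.5% to 5/40 = 12.5% after the first cycle.

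**BBI608, Arm A, patients who have surgery and reach combination therapy**

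Inputs: 960 mg/day, run-in of r days plus a half-day dose on the day of surgery, restart s days after surgery, k combination cycles. Intended DI is 960 × 7 = 6,720 mg/week in both the run-in and the combination cycles, so using the period or the cycle version makes no difference.

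- Span = r + s + 28k days.
- Dose = 960 × (r + 0.5 + 28k) mg.
- Overall RDI = (r + 0.5 + 28k) / (r + s + 28k).

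With r = 7 and s from 28 down to 15:

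- k = 1: 35.5/63 = 56.3% to 35.5/50 = 71.0%.
- k = 6: 175.5/203 = 86.5% to 175.5/190 = 92.4%.
- Run-ins of 5 to 9 days widen the one-cycle range to 33.5/61 = 54.9% to 37.5/52 = 72.1%.

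Arm B BBI608 has a span of 28k days and 28k days of dose, so it scores 100%.

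**Daily compliance, item 4**

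- If computed over the whole span, the same Arm A patient (r = 7, k = 1) reaches at least 960 mg on 35/63 = 55.6% to 35/50 = 70.0% of days.
- If the BBI608-plus-TMZ group starts at combination Cycle 1 Day 1, the hold drops out and the value is 28/28 = 100%.
- Pre-surgery, whole days are divided by 7.5: 7/7.5 = 93.3% for at least 960 mg, and 8/7.5 = 106.7% for at least 480 mg and for non-zero dose. Over run-ins of 5 to 9 days the values are 5/5.5 = 90.9% to 9/9.5 = 94.7%, and 10/9.5 = 105.3% to 6/5.5 = 109.1%.

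**The case against.** **The output is optional and the TMZ input is incomplete.** The SAP says exposure may be summarized as dose received, as dose relative to intent, or both. It never states a TMZ intended cumulative dose, so TMZ RDI needs a figure from the schedule. This stands, and it is why the point applies only if overall RDI is reported. But the SAP gives a TMZ dose unit alongside the RDI definitions, so TMZ dose intensity is evidently contemplated.

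**A sensible programmer might choose a different duration.** Summing 5-day cycles (5k days) would return 100% for TMZ, but it contradicts the written calendar definition. Using four weeks in intended DI alone does not help: RDI becomes 28k/(28(k−1)+5), which is 28/5 = 560% after one cycle.

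**Daily compliance may escape.** A reader might infer that fully adherent Arm A patients will be placed in the lowest category, below 60%. The documents do not establish that. Item 4 summarizes the pre-surgery period separately, so the other group can be read as starting at combination Cycle 1 Day 1. The SAP does not say which, so the whole-span figures are conditional.

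**The half-day effect is cosmetic at full adherence.** A reader might infer that it misclassifies patients. Every full-adherence value above stays in the SAP's category of 90% or more. Only the individual percentage looks odd.

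**Conclusion.** The point holds for two quantities: overall TMZ RDI, and overall BBI608 RDI in Arm A patients who have surgery and go on to combination therapy. The TMZ figures assume constant 150 mg/m², no delay, the derived 750 mg/m² per cycle and a span starting at the first TMZ dose. The shortfall then begins at cycle 2. If the span starts at run-in day 1, it begins at cycle 1 in Arm A. The Arm A BBI608 figures assume 480 mg twice daily, no missed dose and a 7-day run-in unless stated otherwise.

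A reader might infer that the whole exposure section is unsound or that efficacy results are affected. Neither follows. By-period and by-cycle BBI608 RDI, by-cycle TMZ RDI on the 5-day cycle, relative dose, dose-based BBI608 compliance and count-based TMZ compliance do not carry these two faults. Protocol 7.3 bases compliance on capsule counts, and SAP 6.1 defines the full analysis set by receipt of one dose, so overall RDI feeds neither. There is no hypothesis test (SAP 4.1). No endpoint, analysis set or decision changes. The point is minor.

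**What to change.** 1. **TMZ DI and RDI.** Start the span at the first TMZ dose. Use a 28-day cycle both for the end of the span and in intended DI, and state the intended cumulative dose as starting level × 5 doses per cycle. Keep 5 days only for counting planned doses. Intended DI is then 750/4 = 187.5 mg/m² per week, and RDI is (750k/4k)/187.5 = 100% for every k. A real delay still shows: two cycles with one 14-day delay span 70 days, and (1,500/10)/187.5 = 80%. Footnote that permitted escalation to 200 mg/m² gives more than 100%, because the intended level is fixed at the start: 1,750/1,500 = 116.7% at two cycles and 5,750/4,500 = 127.8% at six.

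2. **Arm A overall BBI608 DI and RDI.** Define the duration as the pre-surgical duration (with its 0.5-day term) plus the combination-period duration, leaving out the days from surgery to combination Cycle 1 Day 1. For a 7-day run-in this gives (7.5 + 28k)/(7.5 + 28k) = 100%. Delays between combination cycles still count. No exclusion applies to patients without surgery.

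3. **Daily compliance, item 4.** State that the BBI608-plus-TMZ group starts at combination Cycle 1 Day 1, or otherwise exclude the hold. Use whole days in the pre-surgery denominator. Count the day of surgery for a threshold only if the planned morning dose at the patient's assigned starting level reaches it. With a 7-day run-in at 480 mg twice daily, full adherence gives 7/7 for at least 960 mg and 8/8 for the other two measures. In a cohort starting at 240 mg twice daily, the day of surgery is left out of the 480 mg measure (7/7) and kept for the non-zero measure (8/8).

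The cost is a few SAP lines and minor programming, with no new data.

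### By-cycle and by-period RDI for BBI608 equal RD by construction, so by-cycle RDI misses delays between cycles; only overall RDI reflects them

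*SAP*

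**What the plan says.** All the definitions are in SAP 8.2.1, under Extent of Exposure.

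- **Purpose.** RD is meant to give dose per week "factoring in dose reductions or interruptions". RDI is meant to do so "factoring in dose reductions, interruptions, or delays". Delays are the only thing RDI is said to add.
- **Actual dose intensity (DI).** By cycle it is "cumulative dose in cycle] / [intended cycle duration in" weeks. By period, for Arm A, it is "cumulative dose in the period]/[intended period duration in weeks".
- **Intended DI.** This is "intended cumulative dose per period/cycle] / [intended number of" weeks in that period or cycle. RDI is 100 times actual DI over intended DI.
- **RD.** This is 100 times the cumulative dose over the intended cumulative dose for the cycle or period. For BBI608 the by-cycle intended dose is the product "intended dose level per day) x (intended cycle duration in days", with the dose level fixed at the start of treatment.
- **Durations.** The intended BBI608 cycle lasts max{28, last dose date − first dose date + 1} days. The Arm A pre-surgical period lasts surgery date − first dose date + 0.5 days. Intended treatment duration, used for the overall figures, runs from the first dose to the start date of the last cycle plus its intended duration, less one day.

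**The concern.** A measure whose stated purpose is to add delays to RD should differ from RD when there is a delay. By cycle and by period the SAP divides by an intended duration in both the numerator and the denominator of RDI, so there is no place for a delay to enter separately. A reader comparing by-cycle RD with by-cycle RDI, and finding them equal, could conclude that cycles started on time when the formulas would give equality in any case.

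Safety and tolerability are the Phase Ib primary objective, and the protocol provides for delayed dosing (Protocol 4.5, 7.2.2 and 7.2.4), so late cycle starts can be expected to occur. What is at stake is how an exposure table is read. No endpoint, analysis set or decision rule uses RDI.

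**Working it through.** The SAP states no RDI figure, so there is none to reproduce. The check is algebra, then worked cases.

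**Identity.** Let C be the cumulative dose, I the intended cumulative dose and W the intended weeks of a cycle or period.

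- Actual DI = C/W
- Intended DI = I/W
- RDI = 100 × (C/W)/(I/W) = 100 × C/I = RD

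A numerical check on 10,000 random BBI608 cycles and 10,000 random pre-surgical periods gave a largest difference of 3e-14 percentage points, which is rounding error.

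**Inputs for the cases.** Dose level 960 mg/day (SAP 4.2.1.1, initial dose) and a 28-day cycle. A full cycle is 28 × 960 = 26,880 mg. Intended DI is 26,880/4 = 6,720 mg/week.

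**Case 1: 7-day hold inside a 28-day cycle.** C = 21 × 960 = 20,160 mg. RD = RDI = 20,160/26,880 = 75%.

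**Case 2: 28 dosing days spread over 35 days within one cycle.** Intended duration = max{28, 35} = 35 days, so I = 35 × 960 = 33,600 mg. RD = RDI = 26,880/33,600 = 80%. The stretch shows, but equally in RD.

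**Case 3: two full cycles, cycle 2 starting 14 days late (day 43 instead of day 29).**

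| Measure | Calculation | Result |
|---|---|---|
| By-cycle RD, each cycle | 26,880 / 26,880 | 100% |
| By-cycle RDI, each cycle | (26,880/4) / 6,720 | 100% |
| Cycle 1 on actual length (42 days) | 26,880/6 = 4,480; 4,480/6,720 | 66.7% |
| Overall RDI | 53,760/10 = 5,376; 5,376/6,720 | 80% |

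For the overall figure, the intended end of treatment is day 43 + 28 − 1 = day 70, so the duration is 70 days, or 10 weeks. With no delay, overall RDI is (53,760/8)/6,720 = 100%.

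**Case 4: six full cycles, each of the five later starts 7 days late.** The last cycle starts on day 1 + 5 × 35 = 176, and the duration is 176 + 28 − 1 = 203 days, or 29 weeks. Overall RDI = (161,280/29)/6,720 = 82.8%. By-cycle RDI is 100% in all six cycles.

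**Alternative reading.** Suppose the intended number of weeks in intended DI is a fixed 4, while actual DI uses the max rule. The identity then fails for cycles longer than 28 days. In Case 2, intended DI = 33,600/4 = 8,400, actual DI = 26,880/5 = 5,376 and RDI = 64% against RD of 80%. That counts the stretch twice, and nothing in the SAP says the two terms differ. Case 3 is unchanged, because each cycle's intended duration is still 28 days.

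**The case against.** A reader might infer that RDI as defined cannot show any delay. The documents do not support that. Overall RDI is defined in the same list, and its duration is built on the actual start date of the last cycle, so gaps between cycles lower it (80% in Case 3, 82.8% in Case 4). A reader might also infer that two identical columns will certainly be reported. That is not certain either: the SAP words the exposure summary as optional, allows RD, RDI or both, and does not name by-cycle summaries in that introductory sentence, although it gives the by-cycle formulas.

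Delays can also be seen elsewhere. Daily BBI608 compliance is divided by intended treatment duration, so zero-dose days between cycles lower it. TEAEs leading to BBI608 or TMZ being held are counted (SAP 8.2.4.1). Toxicity delaying treatment by 14 days or more is a DLT criterion (Protocol 4.5), and DLTs are listed. The blood-count rule for starting the next cycle is written for TMZ (Protocol 7.2.2), and the SAP defines TMZ cumulative dose only overall, so by-cycle RDI is in effect a BBI608 measure.

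All of this stands, and it limits the point. It does not remove it. Overall RDI cannot show which cycle was late. The planned-dose denominator of overall RD is not defined: in Case 3, overall RD is 100% if planned dose is summed over cycles and 80% if it is dose level times intended treatment duration, so the contrast with overall RDI is uncertain. In Arm A, read literally, the overall duration also includes the planned 15-28 day post-operative break. An adherent patient with surgery on day 8 (7.5 run-in days) and two on-time cycles has 63.5 dosing days over 78 to 91 days, an overall RDI of 81.4% to 69.8% with no delay at all.

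**Conclusion.** The point holds in limited form. By-cycle and by-period RDI for BBI608 are the same number as RD, and a delay between cycles never appears in by-cycle RDI, contrary to its stated purpose. In the 14-day example the by-cycle figure is 100% where the actual cycle length gives 66.7%; the SAP's overall RDI gives 80%.

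This assumes that the intended duration in actual DI and the intended number of weeks in intended DI are the same quantity, which is the natural reading. The failure to register a between-cycle gap does not depend on that assumption. The examples also assume full dosing at 960 mg/day. The consequence is minor: a descriptive summary in a study with no hypothesis testing (SAP 4.1).

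**What to change.** For BBI608 combination cycles, define by-cycle actual DI as cumulative dose divided by the actual cycle length in weeks. The actual length is the first dose date of the next cycle minus the first dose date of this cycle. For the last cycle, keep max{28, last dose date − first dose date + 1}.

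Keep the planned 28 days in intended DI, for both the intended dose and the weeks (26,880 mg / 4 weeks = 6,720 mg/week), so that a long cycle is not counted twice. Case 3 then gives 66.7% for cycle 1. Case 2, with the next cycle starting on day 36, gives (26,880/5)/6,720 = 80%.

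Leave the Arm A pre-surgical duration as it is. Running it to the next dose would count the planned post-operative break as a delay: 7.5 × 960 = 7,200 mg over 22 to 35 days is about 2,291 to 1,440 mg/week, an RDI of about 34% to 21% in a fully adherent patient. By-period RDI for that period will go on equalling RD, and one of the two can be dropped there.

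In the same edit, define the planned dose in overall RD. The cost is SAP wording and a small programming change; the dosing dates are already used in the SAP's own definitions.
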